Despite multiple options for colorectal cancer (CRC) screening, including several proven to reduce CRC mortality, population-level participation rates are suboptimal. In 2015, it was estimated that only 62% of Americans aged 50-75 were up to date with screening, which is substantially lower than the 80% by 2018 screening goal set by the National Colorectal Cancer Roundtable and endorsed by the American Society of Gastrointestinal Endoscopy.¹ The US Multi-Society Task Force (USMSTF) recommends colonoscopy and fecal immunochemical testing (FIT) as Tier 1 screening tests,² but barriers to completing these tests have been well-characterized.³ For colonoscopy, patient barriers include an aversion to the bowel preparation process, loss of a workday, and the invasive nature of the procedure. For FIT, the main patient barrier is a reluctance to handle stool samples. Although blood-based tests are not currently recommended in the screening guidelines, they overcome all of these known barriers and may substantially improve adherence to screening. Epi proColon is an FDA-approved blood test that detects methylated Septin9 DNA, which is increased in individuals with CRC. The test is indicated for average-risk individuals who have declined guideline-recommended screening options, such as colonoscopy and FIT. Guidelines suggest that patients who decline these Tier 1 options should be offered Tier 2 or 3 options such as sigmoidoscopy, stool-DNA, CT colonography, and capsule colonoscopy. However, since these lower-tier tests face the same patient barriers as the Tier 1 tests and are less widely available, individuals who have declined both colonoscopy and FIT constitute the *de facto* target population for the blood test. Studies have shown that patients who are offered a choice between the blood test and FIT prefer and have higher compliance to the blood test,^{4,5} but it is unknown what proportion of "screen-resistant" patients who have declined *both* colonoscopy and FIT will accept the blood test. This is the crucial question that will determine the potential role of the blood test in the CRC screening landscape.

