
Our prior work has shown that adherence to fecal testing declines rapidly with successive rounds of screening,¹² which highlights the potential of a blood-based test with high-compliance for capturing non-adherent individuals. The performance of the Septin9 blood test was first studied in 7941 asymptomatic individuals, which found an age-standardized 48% sensitivity and 92% specificity for CRC.¹³ These results were based on an assay that defined test positivity as one of two samples with a positive result. A subsequent study has shown that redefining test positivity as one of three samples with a positive result yielded 68% sensitivity and 79% specificity for CRC.¹⁴ The current FDA-approved Epi proColon assay uses three samples. In a trial that compared the blood test to FIT in individuals who were either recently diagnosed with

PROTOCOL TITLE: Assessing the effect of offering a blood-based colorectal cancer screening test

CRC or were undergoing screening colonoscopy, the blood test was found to be non-inferior to FIT with respect to sensitivity (73% vs. 68%) for CRC but had lower specificity (82% vs. 97%).¹⁵ Two studies have evaluated uptake of the blood test compared to FIT. In a German study of 109 individuals who refused screening colonoscopy, 83% chose the blood test and 15% chose FIT. In a multi-center randomized controlled trial conducted in the US, patients who were overdue for screening were assigned to either the blood test or FIT. Test completion rate was 99.5% for the blood test and 88% for FIT. Of the 30 individuals who had a positive blood test, 20 (67%) scheduled or completed a diagnostic colonoscopy within 3 months.

4) Inclusion and Exclusion Criteria

Inclusion criteria (based on review of the electronic health record):

- Age 50-75
- Declined CRC screening (both colonoscopy and FIT) in the previous 6 months, which must be documented in the electronic health record

Exclusion criteria (based on review of the electronic health record data and self-reported questionnaire data):

- Personal history of colonic adenomas (including sessile serrated adenomas), proximal hyperplastic polyps, CRC, inflammatory bowel disease, or hereditary gastrointestinal cancer syndrome
- First degree relative with CRC diagnosed at <60 years of age; family history of hereditary gastrointestinal cancer syndromes.

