The proposed study is a randomized controlled trial that will 1) assess the uptake of a CRC screening blood test among patients who have declined both colonoscopy and FIT in the previous 6 months, including diagnostic evaluation of positive results and 2) survey patients about their beliefs and attitudes regarding CRC screening and testing options. All participants will be primary care patients at the VA NY Harbor Health Care System. Based on a recent internal audit, there were 1502 patients who had at least one primary care visit from August 2016 through August 2017 and were not up to date with CRC screening. Up to date CRC screening is defined as either 1) a colonoscopy within the past 10 years or 2) FIT within the past year. We will perform an updated CRC screening audit at the beginning of the study to obtain the entire pool of eligible patients who are not up to date with screening. Eligible patients will then be randomized 1:1 to either an intervention group or a control group. All patients will receive a letter noting that they are not up to date on screening and encouraging them to contact a study number if they choose to screen with colonoscopy or FIT. Patients who call will speak to a research assistant who is trained in patient navigation and can facilitate referrals for colonoscopy or FIT. Following the sequential testing approach, letters addressed to the intervention group will also include an option to participate in the blood test, with instructions to call the study number to schedule the blood draw. In addition to the letter, both groups will also receive a follow-up telephone call that reiterates information in the letter. The research assistant will make and receive all calls using a standard script. All patients will also be asked to complete a questionnaire about their beliefs and attitudes regarding CRC screening (see Appendix). The questionnaire will be mailed with the invitation letter and will also be administered over the telephone by the research assistant. The study team will notify patients and their primary care physicians of blood test results and will facilitate a colonoscopy referral for those with positive tests. Primary care physicians will not be asked to notify the patients or make the colonoscopy referral because most will not have adequate knowledge of the Septin9 test to provide appropriate patient education.

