The proposed study contains minimal risk. All participants in the study are due for colorectal cancer screening and will receive a letter stating this and encouraging them to screen with either colonoscopy or FIT. These are considered standard of care clinical tests. For the intervention group, the blood-based screening test is also presented as an alternate option. This is a FDA-approved test, although it is currently not available in the VA. Individuals in the intervention group who choose to undergo the blood test would undergo a single blood draw. A final risk is that of breach in patient confidentiality.

15) Potential Benefits to Subjects

Nearly 20% of age-eligible veterans cared for at the VA NY Harbor Health Care System are not up-to-date on colorectal cancer screening. The introduction of a non-invasive test that also does not involve handling stool may increase participation in screening in this refractory population.

16) Vulnerable Populations

Vulnerable populations will not be enrolled.

17) Sharing of Results with Subjects

The study team will share the results of the blood test with patients by telephone or mail and notify their primary care physicians using a CPRS note.

18) Setting

Study recruitment and phlebotomy will be performed at the VA NY Harbor Health Care System. The lab assay will be performed offsite at a commercial laboratory because the equipment is not available onsite.

19) Resources Available

The Principal Investigator (PI) is a board-certified gastroenterologist and clinical researcher with expertise in colorectal cancer screening. He has master's level training in epidemiology and biostatistics and is able to perform all of the planned analysis.

The research assistant will be credentialed in phlebotomy and trained by the PI in principles of patient navigation.

The PI has the full support of the Epigenomics, which makes the blood-based test. Epigenomics has agreed to cover the cost of the study.

PROTOCOL TITLE: Assessing the effect of offering a blood-based colorectal cancer screening test

20) Confidentiality

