14) Have you ever had a stool-based test (e.g. fecal occult blood test/FOBT or fecal immunochemical test/FIT)?

Yes No (SKIP to 15)

14a) How long ago was your last stool-based test?

Less than 12 months More than 12 months

15) Why did you decide not to do a colonoscopy when offered in the past 6 months?

I don't want to take the bowel prep
I don't want to know if I have colorectal cancer
Colonoscopy is painful
I don't have time
I don't have an escort
I'm at low risk and don't need screening
Other
I wasn't offered the test in the past 6 months

16) What would make you change your mind and get a colonoscopy?

If the bowel prep were easier
If I knew colonoscopy can prevent cancer by removing pre-cancerous polyps
Overcoming my fears about colonoscopy
If my doctor recommended it
If I knew it wasn't going to hurt
If I had time/could get time off from work
If I could find an escort
Other
Nothing would change my mind

17) Why did you decide not to do a stool test (fecal immunochemical test/FIT) when offered in the past 6 months?

I don't want to handle stool
I don't want to know if I have colorectal cancer
The directions for the stool test was too complicated
I don't think a stool test is accurate
I don't have access to a toilet that's suitable for collecting the stool sample
Other
I wasn't offered the test in the past 6 months

18) What would make you change your mind and take a stool test?

If the directions for the stool test was easier to understand
If I knew the stool test was accurate
If I had access to a toilet that's suitable for collecting the stool sample
Other
Nothing would change my mind

PROTOCOL TITLE: Assessing the effect of offering a blood-based colorectal cancer screening test

19) Would you take a blood test to screen for colorectal cancer?

Yes No (SKIP to 22)

20) Why would you take the blood test?

A blood test is easy/convenient
 A blood test is not painful
 A blood test is accurate
 Other

21) What do you think are the advantages of a blood test compared to colonoscopy and stool test?

It's more convenient than a colonoscopy or a stool test
 I don't have to do any special preparation to take the test
 I'm used to getting blood tests
 I think blood tests are more accurate than other tests
 The test is done by a medical professional and I don't have to do anything myself
 Other

22) Why would you not take a blood test?

I don't like getting my blood drawn
 I don't think a blood test is as accurate as a colonoscopy or stool test

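### The audit's up-to-date rule recognises only colonoscopy and FIT, so a patient current by another test the protocol names could be randomised as screen-resistant

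*Combined protocol and SAP*

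**What the plan says.** Section 9 (Procedures Involved) defines who is current: "Up to date CRC screening is defined as either 1) a colonoscopy within the past 10 years or 2) FIT within the past year". The pool is built from that rule: "We will perform an updated CRC screening audit at the beginning of the study to obtain the entire pool of eligible patients". Eligible patients are then randomised 1:1 and mailed a letter saying they are behind on screening.

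Section 4 (Inclusion and Exclusion Criteria) adds a second condition: "Declined CRC screening (both colonoscopy and FIT) in the previous 6 months, which must be documented in the electronic health record". Its exclusions cover personal history ("Personal history of colonic adenomas (including sessile serrated adenomas), proximal hyperplastic polyps, CRC, inflammatory bowel disease, or hereditary gastrointestinal cancer syndrome"), family history, severe comorbidity and vulnerable groups. None concerns screening by another test.

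The protocol recognises other tests. The opening section, before 3) Background, reports that guidelines suggest people who decline the two Tier 1 tests "should be offered Tier 2 or 3 options such as sigmoidoscopy, stool-DNA, CT colonography, and capsule colonoscopy". Item 14 of the appended questionnaire puts FOBT beside FIT: "Have you ever had a stool-based test (e.g. fecal occult blood test/FOBT or fecal immunochemical test/FIT".

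Section 14 (Risks to Subjects) says of the whole trial population: "All participants in the study are due for colorectal cancer screening and will receive a letter stating this".

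**The concern.** The trial is about people who refuse screening. The audit rule in fact finds people who lack two particular tests. A patient who recently had, say, stool-DNA testing or CT colonography elsewhere is not up to date under Section 9. That patient also has an obvious reason to turn down colonoscopy and FIT when next offered them, and so could satisfy Section 4 as well.

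Three things would be at stake:

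- **Dilution.** Such patients have little reason to take any further test in either arm. Both screening rates, the blood-test uptake and the difference between arms would shrink.
- **Labelling.** The result is meant to describe screen-resistant patients, and the survey in Aim 2 is meant to explain why they refuse. People already screened belong to neither picture.
- **The letter.** Some recipients would be told they are overdue when a test the protocol lists as a guideline option still covers them.

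**Working it through.** **Step 1. Trace a patient through the rules.** Take a patient aged 50-75, current by one of the other named tests, with no colonoscopy in 10 years and no FIT in the past year.

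1. Section 9 audit: not up to date, so the patient enters the pool.
2. Section 4 inclusion: met if the record shows that colonoscopy and FIT were both declined in the previous 6 months, whatever the reason.
3. Section 4 exclusions: none applies.
4. Questionnaire: Section 4 lets exclusions draw on self-report. But the form is mailed with the invitation, after randomisation; Section 23 (Consent Process) calls it anonymous; and no listed exclusion would use the answer. Items 15 and 17, on reasons for declining, offer no already-screened answer other than Other. The earlier items are not in the text available for this review, so nothing is concluded about them.

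The written rules therefore let this patient through.

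**Step 2. Reproduce the planned sample size.** Inputs from Section 11 (Sample Size Calculations): uptake 50%, difference 15 points, alpha 0.05, power 80%. The control rate is not stated; 35% is inferred as 50% minus 15 points. With a two-sided test, pooled variance and no continuity correction:

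n = [1.96 × √(2 × 0.425 × 0.575) + 0.8416 × √(0.50 × 0.50 + 0.35 × 0.65)]² / 0.15²

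= (1.370 + 0.582)² / 0.0225 ≈ 169.3, so 170 per group.

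This matches the plan. (50% against 65% also gives 170.) Power is 80.2% at 170 and 82.4% at 180 per group.

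**Step 3. Dilute.** The documents give no value for f, the share already screened by another test, so a range is assumed. Suppose these patients take no further test in either arm, and the rest behave as planned:

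- intervention rate = 50(1-f)%
- control rate = 35(1-f)%
- difference = 15(1-f) points

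Power = Φ{[d√n - 1.96√(2p̄(1-p̄))] / √(p₁(1-p₁) + p₂(1-p₂))}, where p₁ and p₂ are the diluted rates, p̄ their mean and d their difference.

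| f | Patients (of 360) | Rates | Difference | Power, 170 per group | Power, 180 per group | n per group for 80% |
|---|---|---|---|---|---|---|
| 0% | 0 | 50.0% v 35.0% | 15.0 | 80.2% | 82.4% | 170 |
| 2% | about 7 | 49.0% v 34.3% | 14.7 | 78.8% | 81.0% | 176 |
| 5% | 18 | 47.5% v 33.25% | 14.25 | 76.6% | 78.9% | 185 |
| 10% | 36 | 45.0% v 31.5% | 13.5 | 72.8% | 75.2% | 203 |

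The 180 column assumes no drop-out. The 170 column is what remains if the plan's allowance is fully used.

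**The case against.** The best case for the plan has four parts.

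**The decline requirement.** Lacking the two tests is not enough for randomisation; a documented decline of both within 6 months is also needed. A chart reviewer might judge that a patient with current screening on file has not declined screening. This stands as a limit on the claim: the text supports could be randomised, no more. It does not close the gap, because the criterion asks only whether the two tests were declined, and being already screened is a natural reason to decline them.

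**The setting.** The opening section says the lower-tier tests meet the same patient barriers and are harder to obtain, and that this site offers colonoscopy and FIT. A two-test audit suits such a site, and the affected group is plausibly small. This also stands, though it does not rule out tests done elsewhere.

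**Consistency.** By Section 9's own definition these patients are due, so Section 14 does not literally contradict it. That is fair. The tension is with the protocol's own list of guideline options, under which the same patient need not be due.

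**Size.** The values of f are assumed, and 15 points is the difference the trial is powered to detect, not a forecast of the effect. Both are correct, so the table is illustration only.

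A reader might go further and infer that the treatment comparison is biased. The documents do not support that. Eligibility is settled before 1:1 allocation, so these patients fall equally into both arms in expectation.

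**Conclusion.** The concern holds in a limited form. Section 9 states a closed rule, not merely an incomplete description, and followed exactly it can admit patients whom the protocol's own account of screening options would not call due. The consequence is mild dilution and a weaker screen-resistant label.

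The illustrated loss at 180 per group is about 1 point of power at f = 2%, 4 at 5% and 7 at 10%. It rests on an inferred 35% control rate, no uptake of any further test among those already screened, and no drop-out. If the blood-test offer raises screening among some of these patients too, the loss in the difference is smaller.

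Two stronger readings should be resisted. First, one might infer that a known number of already-screened patients is being enrolled; the documents give no count, and 18 is simply 5% of 360. Second, one might infer that the 6-month screening outcome should be widened to the same list of tests. A gap in baseline eligibility does not justify changing how the primary endpoint is counted. The waiver requested in Section 23 for following control patients also reaches only colonoscopy and FIT.

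This is a desirable improvement, not a threat to the trial's main comparison.

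**What to change.** At the pre-randomisation audit, also check each otherwise eligible patient's record for sigmoidoscopy, stool-DNA, CT colonography, capsule colonoscopy or FOBT, including outside results filed there. Exclude patients whose test is still current, before allocation. The sponsor must specify the interval for each test, because the documents give intervals only for colonoscopy and FIT. Section 9's definition and Section 4's exclusions should then carry the same wording, which would bring practice into line with the statement in Section 14. Leave the 6-month outcome definition unchanged.

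The cost is a few more items in a chart review already planned, and a slightly smaller pool. Section 23 already requests a waiver for eligibility screening. The earlier audit found 1502 patients not up to date for 360 places, although that count precedes the decline requirement and the exclusions, so the true margin is not known. Tests done elsewhere and never filed in the record would still be missed. The check should come before randomisation, since affected patients cannot be removed as cleanly afterwards.

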- Patients with severe comorbidities who may not benefit from CRC screening due to limited life expectancy (e.g. poorly controlled or end-stage neurologic, cardiac, pulmonary, renal, or oncologic disease).
- Vulnerable populations
 - Adult unable to consent
 - Individuals who are not yet adults (infants, children, teenagers)
 - Pregnant women
 - Prisoners

5) Study-Wide Number of Subjects

This is a single site study with a total enrollment of 360 patients. 180 patients each will be in the intervention and control groups, respectively.

6) Study-Wide Recruitment Methods

All participants will be primary care patients within the VA NY Harbor Health Care System. We will perform an updated CRC screening audit at the beginning of the study to obtain the entire pool of eligible patients who are not up to date with screening. Eligible patients will then be randomized 1:1 to either an intervention group or a control group. All patients will receive a letter noting that they are not up to date on screening and encouraging them to contact a study number if they choose to screen with colonoscopy or FIT. Patients who call will speak to a research assistant who is trained in patient navigation and can facilitate referrals for colonoscopy or FIT. Following the sequential testing approach, letters addressed to the intervention group will also include an option to participate in the blood test, with instructions to call the study number to schedule the blood draw. In addition to the letter, both groups will also receive a follow-up telephone call that reiterates information in the letter. The research assistant will make and receive all calls using a standard script.

PROTOCOL TITLE: Assessing the effect of offering a blood-based colorectal cancer screening test

7) Study Timelines

Each individual who is enrolled in this study will participate for a maximum of 6 months. We anticipate enrollment will take approximately 9 months. From the time that the study is approved, we estimate that it will take 18 months to complete the primary analysis.

8) Study Endpoints

Aim #1: *To measure screening uptake with a blood test in screen-resistant patients who have declined both colonoscopy and FIT at VA NY Harbor Health Care System.* Using the approach outlined above, we will identify and randomize 360 eligible patients, with 180 patients each in the intervention and control groups (see Sample Size Calculations).

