Primary outcome: Screening rate in the intervention group vs. control group after 6 months.

Secondary outcomes:

A) Complete screening rate in both groups, which is defined as completion of the entire screening strategy. For colonoscopy, this requires cecal intubation and an adequate bowel preparation. For individuals who took Septin9 and FIT, positive results must be followed by a colonoscopy with cecal intubation and adequate bowel preparation.

B) Among individuals in the intervention group who had a positive blood test, proportion who completed a follow-up colonoscopy within 6 months.

C) Endoscopic and pathologic findings among individuals in the intervention group who had a diagnostic colonoscopy.

Aim #2: *To survey screen-resistant patients to understand their beliefs and attitudes about CRC screening and testing options.* Both intervention and controls groups will be invited to complete a brief questionnaire. Questionnaire questions are shown in the Table and are adapted from a previous study that offered both the blood test and FIT to patients who had refused screening colonoscopy.⁴ All response options will be presented in a multiple-choice format. The full questionnaire is shown in the Appendix.

Primary outcome: Demographic and health-related predictors of accepting the blood test in the intervention group.

Secondary outcomes:

A) Proportion of both groups who answered that they would be willing to take a blood test for colorectal cancer screening

B) The most commonly cited advantages of a blood test compared to colonoscopy and stool test in both groups

C) The most commonly cited reasons for not taking the blood test in the intervention group. In an exploratory analysis, we will stratify results by race/ethnicity, self-reported health, frequency of healthcare access, and self-perceived risk of CRC.

Table. Select Questionnaire Questions

Demographics
What is your age?
What is your race?
What is your ethnicity?
Health status and medical history
How would you rate your overall health?
How many visits have you had with your primary care doctor in the past year?
What do you think is your own risk of getting colorectal cancer?
Colorectal cancer testing
Have you ever had a colonoscopy? If so, when?
Have you ever had a stool-based test? If so, when?

PROTOCOL TITLE: Assessing the effect of offering a blood-based colorectal cancer screening test

Why did you decide not to do a colonoscopy when offered in the past 6 months?

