Participants who are randomized to the blood test arm will undergo phlebotomy, which will be performed by the study research assistant. The blood sample will be temporarily stored on-site and then transported to an off-site commercial laboratory to run the assay.

Clinical outcomes for both the intervention and control group participants will be measured as a secondary outcome. This includes timing and result of a screening colonoscopy or FIT for individuals in the controls group as well as diagnostic colonoscopy for participants who had a positive blood test.

PROTOCOL TITLE: Assessing the effect of offering a blood-based colorectal cancer screening test

10) Data and Specimen Banking

Blood specimens for individuals in the intervention group will be assayed but not stored. No data other than what is described in the sections above will be stored.

11) Data Management

Blood specimens will be transported and assayed by an outside commercial laboratory. Result will then be uploaded to the electronic medical record.

All personnel who will be working on this project will have completed the necessary CITI and TMS training for research involving patient data. Data will be collected from the electronic medical record, which only individuals credentialed by the VA can access using password-protected accounts. All data collected will be compiled in a password-protected spreadsheet, and sharing of data will be restricted to the study personnel listed on the proposal using VA email. After data has been collected from the electronic health record, the data will be de-identified prior to analysis.

Data Analysis

Aim 1: Screening rates in the intervention vs. control groups will be compared using the chi-squared or Fisher's exact test. Clinical outcomes of individuals who took the blood test will be reported as descriptive statistics.

Aim 2: We will use a multivariable logistic regression model to assess demographic and health-related predictors of accepting the blood test. We will perform descriptive statistics to assess the secondary outcomes. Results for secondary outcomes will also be reported stratified by race/ethnicity, self-reported health, frequency of healthcare access, and self-perceived risk of CRC.

Sample Size Calculations

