Aim 1: Two prior studies that have measured uptake of the Septin9 blood test have found very high rates of 84% and 99%, respectively.^{4,5} The study that found 84% uptake involved patients who had previously declined colonoscopy and were subsequently given a choice between the blood test and FIT. Since our study population has previously declined both colonoscopy and FIT, their uptake of the blood test will likely be lower. We estimate that uptake in our population will be 50% and will power our study to detect a 15% absolute difference in screening rate. With alpha = 0.05 and 80% power, the required sample size in each group is 170. To account for drop-out, we will include 180 patients in each group.

Aim 2: Assuming a 50% uptake in the intervention group of 170 individuals, there will be an estimated 85 individuals who take the blood test. We will select variables with the strongest association with blood test completion on bivariate analysis, which will be entered into the final multivariable logistic regression model. The number of variables in the final model will be limited to ensure that there are at least 10 events per variable, which is the conventional minimum standard to preserve model validity.¹⁶

12) Provisions to Monitor the Data to Ensure the Safety of Subjects

We believe this study poses no more than Minimal Risk to study participants, and therefore there are no plans to establish a data monitoring committee. However, any unexpected adverse events will be reported immediately to the PI, who will report to the IRB on an ad-hoc basis.

PROTOCOL TITLE: Assessing the effect of offering a blood-based colorectal cancer screening test

13) Withdrawal of Subjects

There are no anticipated circumstances under which subjects will be withdrawn from the research without their consent. Participants may choose to withdraw from the study at any point by giving notification to the study team. Patients who withdraw from the study will no longer be tracked in the electronic medical record after the time of withdrawal.

14) Risks to Subjects

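### The primary comparison is an unadjusted test with no effect estimate, although at least age is read from the record before randomisation; a prespecified adjusted risk difference would serve better

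*Combined protocol and SAP*

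**What the plan says.** Section 8 (Study Endpoints, Aim 1) defines the endpoint: "Primary outcome: Screening rate in the intervention group vs. control group after 6 months". The whole analysis of it is in section 11 (Data Analysis, Aim 1): "Screening rates in the intervention vs. control groups will be compared using the chi-squared or Fisher's exact test". No risk difference, ratio, confidence interval, covariate or rule for choosing the test follows. The only regression planned is for Aim 2, where it models acceptance of the blood test and not the comparison of arms.

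The sample size paragraph for Aim 1 works on the absolute scale: "We estimate that uptake in our population will be 50% and will power our study to detect a 15% absolute difference in screening rate", then "With alpha = 0.05 and 80% power, the required sample size in each group is 170", then "To account for drop-out, we will include 180 patients in each group". It states neither the control rate, nor the sidedness, nor the test.

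On what is known before allocation, section 4 bases the inclusion criteria (age 50-75 and documented refusal of both tests) on review of the electronic health record. Section 9 applies a screening-history check: "Up to date CRC screening is defined as either 1) a colonoscopy within the past 10 years or 2) FIT within the past year". Only then, in sections 6 and 9: "Eligible patients will then be randomized 1:1 to either an intervention group or a control group". No stratification is described.

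**The concern.** There are three related gaps.

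- **No estimate.** The study asks how much offering a blood test raises screening, and it is sized on a 15-point absolute difference. A test alone gives a p-value and no answer on that scale.
- **Unused baseline information.** Age is known for every patient before randomisation, and some screening history has been consulted. If such variables predict screening, prespecified adjustment gives a more precise estimate of the same marginal risk difference. If they do not, little is lost.
- **An open choice of test.** The two named tests can disagree. With 90 of 180 screened in one arm and 71 of 180 in the other, uncorrected chi-squared gives p = 0.044 and Fisher's exact test p = 0.056. The choice should not remain open once data are seen, particularly as section 19 says that the test's manufacturer covers the study cost and that the principal investigator is able to perform all of the planned analysis.

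**Working it through.** **Inputs.** Intervention rate 50%, difference 15 points, alpha 0.05, power 80%, 170 then 180 per group (Sample Size Calculations, Aim 1). A control rate of 35% is implied if 50% is read as the intervention screening rate. Two-sided testing is an assumption, supported by the reproduction below.

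**1. The plan's own figure.** Pooled-variance formula without continuity correction, with mean rate 0.425:

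n = [1.960 × √(2 × 0.425 × 0.575) + 0.842 × √(0.50 × 0.50 + 0.35 × 0.65)]² / 0.15²

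= [1.960 × 0.699 + 0.842 × 0.691]² / 0.0225 = 169.3, rounded up to **170**.

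The stated figure is reproduced. One-sided testing would give 134 and a continuity correction 183, so 170 fits an uncorrected two-sided chi-squared test.

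**2. Exact power of the two named tests.** Full enumeration of both binomials, two-sided 0.05:

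| Rates | n per group | Chi-squared, uncorrected | Fisher |
|---|---|---|---|
| 50% vs 35% | 170 | 80.9% | 77.9% |
| 50% vs 35% | 180 | 82.1% | 79.2% |
| 40% vs 25% | 180 | 86.5% | 83.8% |
| 35% vs 20% | 180 | 89.7% | 87.2% |
| 25% vs 10% | 180 | 96.9% | 95.8% |

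At 50% vs 35% and 180 per group, the chi-squared test is significant and Fisher's is not in about 82.1 − 79.2 = 2.9% of trials.

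**3. Is Fisher's test needed?** The smallest expected count at the planning rates is 180 × 0.425 = 76.5. Even at 25% vs 10% it is 180 × 0.175 = 31.5. The usual small-count reason does not arise.

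**4. Precision of the unadjusted estimate.** The 95% CI half-width at 180 per group is 1.96 × √[(0.25 + 0.2275)/180] = 0.101, about 10 percentage points.

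**5. What adjustment could add.** The documents give no covariate strength, so this is a range. For a standardised risk difference from a logistic model with one normal baseline score X, the large-sample variance is

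{E[p₁(X)(1 − p₁(X))] + E[p₀(X)(1 − p₀(X))]}/n + Var[p₁(X) − p₀(X)]/(2n),

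set against (0.25 + 0.2275)/n unadjusted.

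| Odds ratio per SD of X | Variance reduction |
|---|---|
| 1.1 | 0.2% |
| 1.2 | 0.8% |
| 1.6 | about 4-5% |
| 2.0 | about 9-10% |

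Reductions of 5% and 10% shrink the half-width to 0.101 × √0.95 = 0.098 and 0.101 × √0.90 = 0.096. They move approximate power at 180 per group from 82.4% to 84.3% and 86.2%.

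**6. Can the model carry the covariates?** Arm plus four covariates is five terms. At 50% vs 35% the expected number screened is 360 × 0.425 = 153. At 25% vs 10% it is 360 × 0.175 = 63, still 12.6 per term. Both exceed the ten events per variable that the plan adopts for Aim 2.

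**The case against.** **The unadjusted test is valid.** Under 1:1 randomisation with no stratification described, nothing is broken, and adjustment is an improvement of unknown size. This stands. If the covariates are weak, the gain is worth less than one point of power.

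**Fisher's shortfall may never occur.** A reader might infer that the trial misses its stated power. The documents do not support that. Naming the two tests together is ordinarily read as Fisher for sparse tables, and the tables here will not be sparse, so chi-squared would be used. At 180 the shortfall would be 0.8 point, and it rests on a control rate that the plan never states. Section 3 reports limited success from promoting colonoscopy and FIT, and every patient has declined both, so lower control rates are plausible; with the same 15-point difference at the lower control rates tabulated above, Fisher also exceeds 80%.

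**The baseline data may not be to hand.** A reader might infer that the audit already holds a full covariate set. It is described only as identifying eligible patients. The 10-year and 1-year windows show that screening history is consulted, but every eligible patient fails both, so only older history could vary between patients. Lifetime testing and visit counts are questionnaire items, not listed audit outputs. Section 23 calls the questionnaire anonymous, and section 9 mails it with the invitation letter, after allocation. Only age is certain.

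**Aim 2 does not identify the predictors.** It selects variables by bivariate association, and it concerns blood-test acceptance in one arm. It shows interest in such predictors, not knowledge of them.

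**Conclusion.** The point holds as an improvement in method. The primary analysis lacks an estimate on the scale on which the study was sized, and it uses no baseline information although at least age is available for everyone before randomisation. A prespecified standardised risk difference remedies both and settles which analysis is primary.

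The sample size is correct for uncorrected two-sided chi-squared at 50% vs 35%, and no power error is claimed. Fisher's test has no justification here and does not match that calculation, but its shortfall is small and conditional on the implied control rate. The precision gain runs from near zero to about 10% of variance for odds ratios per SD up to 2.0. That range is assumed, not drawn from the documents.

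**What to change.** In section 11, Data Analysis, Aim 1:

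- Make the primary estimate the standardised difference in the proportion screened within 6 months, with a robust 95% CI, from a logistic regression on arm and prespecified covariates.
- Take the covariates from the health record as it stood before randomisation: age in any case, plus prior colonoscopy, prior stool test and primary care visits in the past year if the record review captures them. Fix the list before allocation, and do not use questionnaire answers.
- Keep the Pearson chi-squared test without continuity correction as the supportive unadjusted analysis, and delete the Fisher option.

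The cost is a few lines of text and a little more analysis, plus one administrative step. Section 10 limits stored data to what the protocol describes, so the covariates must be listed there. Section 23 requests the control-arm waiver for determining colonoscopy or FIT within 6 months, so retaining baseline variables on patients who give no written consent should be checked against it. If only age can be kept, adjust for age alone; the risk difference and its interval are still gained.
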